
9.5 Informed Consent/Assent and HIPAA Authorization

At entry into the study, parent(s) or legal guardian of the subjects will be asked to review the study informed consent form (ICF). The Project Coordinator or other member of the clinical research team will meet with the family on Day 1 of Visit 1 to review the form, to confirm the subject understands the study, and to answer any questions that the subject or parent/guardian might have. After all study-related questions are answered and subjects and families have had time to consider their decision, the Project Coordinator or member of the clinical research team will obtain fully informed, written consent from parent(s) or legal guardian of the subjects. Again, in the event of enrollment of a non-English speaking subject/family, an interpreter will be used to present the study and the consent document in a language understandable to the family. The main ICF will include a Study Summary Document for interpreter documentation attesting to statements on the summary document, If the interpreter is not in person but is instead conferenced in by phone, then a copy of this attestation document will be faxed or emailed (using secure email) to the interpreter to sign and return to the team electronically. The consent will be signed in the presence of a team member. The families will be given a printed copy of the signed, informed consent. The subjects will be too young to assent to this study.

9.5.1 Waiver of Documentation of Consent/Assent and Alteration of HIPAA Authorization

Full waivers of consent will only be sought for the verbal screening component of the study. The rights and welfare of the subject will not be adversely affected because during the verbal consent process it is explained to the subject that we are recording their health information to determine eligibility for the study. Study staff stress during the verbal consent that the screening is voluntary, but necessary if they wish to participate, and that they can decline and stop the process at any point. A written informed consent will be obtained upon study entry before any study procedures are performed.

9.6 Payment to Subjects/Families

We will compensate subjects/families via bank card (ClinCard) at a standard rate of \$150 per research visit day to offset incurred expenses, including compensation for time, food, and babysitting expenses. The baseline and 12-week visits will require 2 or 3 days and one or two overnight stays to complete the protocol. For the baseline (Visit 1) and 12 week (Visit 3) visits, we have assumed that half the families will receive \$150 to complete the visit and study protocol procedures and half will require an additional day to complete procedures, and will receive \$300. For the 6-week visit (Visit 2), all families will receive \$150 as an additional day will not be an option. The average compensation to complete the study is \$600, with a minimum of \$450 and maximum compensation of \$750. If the subject/family total compensation exceeds \$600 in one calendar year, they will be provided with a W9 form.

	Each Visit	If Additional day required
Visit 1 (Baseline)	\$150	\$300
Visit 2 (6-weeks)	\$150	\$150*
Visit 3 (12 weeks)	\$150	\$300
	\$450 (minimum)	\$750 (maximum)

*The compensation for Visit 2 (6 weeks) will always be \$150 as there is no additional day option.

Subjects/Families will be compensated \$150 for each visit for your time and effort associated with the study protocol procedures. Since one important test (sleeping energy expenditures [SEE]) for this Baseline Visit 1 requires you to be very still, it is planned to be conducted during a nap. If the SEE is not completed in one day than an additional day may be needed.

If subjects are not local to CHOP, they will stay in a nearby hotel for either 1 or 2 nights depending upon time of research procedures and whether a Day 3 is needed to complete the SEE. Subjects will also be reimbursed to cover the costs of travel and parking Subjects/ families will provide official receipts for these items. The 12-week Visit 3 plan is the same as Visit 1. The 6-week Visit 2 requires one day of research study procedures.

For all subjects not from the Philadelphia area, we have assumed that the cost of travel will paid for the subject and one family member to accompany the subject for about half of the subjects and for two people to accompany the subject for the other half of subjects. The overnight stays will also be paid for the family at a hotel nearby to CHOP.

Travel expenses that are considered reimbursable are: miles to/from CHOP for subjects who are traveling regionally (miles to/from the airport or train station, parking at the airport or train station (at a rate of \$20/day), cab to and from the airport or train station, checked bags. All expenses will be reimbursed with official receipts by bank card (ClinCard) payment request.

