3.3 Study Population

3.3.1 Inclusion Criteria

- Cystic fibrosis with at least one CFTR gating mutation of these ten (G551D, G178R, S549N, S549R, G551S, G1244E, S1251N, S1255P, G1439D, or R117H).
- Age: 6 months to 2 years of age
- In their usual state of good health
- A clinical decision has been made for subject to begin ivacaftor treatment.
- Family committed to the 4 to 6 month study protocol with visits to CHOP that will last 2-3 days for the baseline visit (Visit 1) prior to ivacaftor treatment and the 12 week visit (Visit 3) after clinically prescribed ivacaftor treatment has begun, and will last up to 2 days for the 6 week visit (Visit 2) after ivacaftor treatment has begun.
- Note that ivacaftor is now approved by the FDA for 6 month to 2 year old children for the additional 28 CFTR mutations known to be responsive to ivacaftor potentiation, these will also be considered. With our limited sample size, the mutations that have shown the strongest improvement with treatment will be given priority for enrollment.

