4.2 Observational Period

Many of the protocol assessments could occur on any of the visit days (i.e. questionnaires, spot stool sample). Below is the best estimate of how each day will proceed. The baseline (Visit 1) and the 12 week (Visit 3) visit after ivacaftor treatment has begun are nearly identical with the exception of obtaining informed consent which will occur at Visit 1 Day 1 prior to any assessments being done or specimens being collected. For the 6 week (Visit 2) and 12 week (Visit 3) visits that will occur after confirmation of the timing of the start of clinically prescribed ivacaftor treatment, there will be a ± 2 week window for the visit. (i.e. 6 week visit may occur between 4 and 8 weeks, and 12 week visit between 10 and 14 weeks post ivacaftor treatment).

The description provided here applies to subjects who are not local to CHOP and who will be traveling to Philadelphia from other regions of the US and Canada and staying at a local hotel for one or two nights depending on the time of their scheduled research procedures. For non-regional families, Day 1 of each Visit is the day of arrival to CHOP and first night of their hotel stay.

If the subject is local to CHOP, we will still require a Day 1 visit for in-person written consent for Visit 1, however, for Visits 2 and 3, Days 1 and 2 can be combined to complete study protocol procedures, and they will come in to CHOP from home for the major study protocol days: Day 2 for Visit 2 and Day 2 and again on Day 3 (if needed) for Visit 3.

• •	Informed Consent/Assent will be completed in at CHOP Main CHPS Instructions in preparation for study procedures will be given Spot stool sample will be collected for Fecal Elastase I and fecal calprotec (collected anytime)
•	Questionnaires may occur on this day (see Day 2 for details)

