4.2.1 Baseline visit (Visit 1)

- Spot stool sample for fecal elastase and fecal calprotectin (if not collected on Day 1)
- Questionnaires: Health History
- Anthropometry: Length, weight, head circumference, skinfolds, circumferences
- •

Day 3 (if needed and expected for half of subjects)

Sleeping energy expenditure test– if it was not performed on Day 2

Post Visit Follow Up

- 3-day weighed food records
- Begin clinically prescribed ivacaftor treatment after food records have been completed, and document the date that ivacaftor treatment was started

In Between Visits 1 & 2

• Maintain adverse events calendar

4.2.2 6 week visit (Visit 2) after ivacaftor treatment has begun

Day 1 Instructions in preparation for study procedures will be given Spot stool sample will be collected for Fecal Elastase I and fecal calprotectin (collected anytime) Questionnaires may occur on this day Day 2 Sleeping energy expenditure with morning nap (or afternoon nap if necessary). Time and amount of food and beverage intake will be recorded prior to the procedure. Anthropometry: Length, weight, head circumference, skinfolds, circumferences

- Blood draw for fatty acids and serum calprotectin
- Spot stool sample for fecal elastase and fecal calprotectin (if not collected on Day 1)
- Questionnaires regarding interval health history, Adherence to ivacaftor, enzymes, medications, and Adverse events

Post Visit Follow Up

- 3-day weighed food records
- Maintain adverse events calendar

In Between Visits 2 & 3

• Maintain adverse events calendar

4.2.3 12 week visit (Visit 3) after ivacaftor treatment has begun

•	Day 1 Instructions in preparation for study procedures will be given Spot stool sample will be collected for Fecal Elastase I and fecal calprotectin (collected anytime) Questionnaires may occur on this day
	Day 2
•	Sleeping energy expenditure with morning nap (or afternoon nap if necessary). Time and amount of food and beverage intake will be recorded prior to the procedure.
•	Blood draw for CBC, CMP, pre-albumin, bile acids, fatty acids, serum calprotectin, vitamin A (retinol), vitamin D (25(OH)D), vitamin E (a-tocopherol) and vitamin K (ucOC)
•	Spot stool sample for fecal elastase and fecal calprotectin (if not collected on Day 1)
•	Questionnaires about interval health history, Adherence to ivacaftor, enzymes, medications, and Adverse events
•	Anthropometry: Length, weight, head circumference, skinfolds, circumferences

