	Day 3 (if needed and expected for half of subjects)

• Sleeping energy expenditure test- if it was not performed on Day 2

Post Visit Follow Up

- 3-day weighed food records
- Maintain adverse events calendar until 3-day food records are completed

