6.1.1 Analysis of Primary & Secondary Aims

Data Analysis: Analysis will begin with descriptive analyses of the study sample using means, standard deviations, medians, and ranges for continuous variables, and frequency distributions for categorical variables. Descriptive statistics and exploratory graphing such as frequencies, means, standard deviations, box plots, and scatter plots will be used to assess the normality of the data in terms of the presence of skew and/or outliers. Primary Aims: The goals of the primary aims of this study are to determine whether ivacaftor treatment improves SEE and BMI Z score. Secondary Aims: The goal of the secondary aim is to determine whether ivacaftor improves gut health and function as measured by total plasma fatty acids, fecal elastase and fecal calprotectin (ug/g stool). Analysis of efficacy for the primary and secondary outcomes will be based on change from baseline (before treatment) in SEE% predicted (Schofield), BMI Z scores, total plasma fatty acids, fecal elastase continuous

outcomes will initially be compared using paired-t-tests if continuous variables are normally distributed and nonparametric tests (Wilcoxon sign rank) if they are not. Subsequently, mixed effects longitudinal models will be performed to assess change over all three time points (baseline, 6 and 12 weeks), adjusting for potential covariates such as age, sex, and adherence to treatment. Chi-squared tests will be used for comparison of categorical variables before and after ivacaftor treatment. Using similar methods, exploratory analyses will examine improvement in dietary intake of calories and fat, in growth status (weight, length, and head circumference Z scores) and growth velocity (both absolute and Z scores), serum fat soluble vitamins, bile acids, and calprotectin.

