Secondary outcomes: A sample of 16 subjects will provide 80% power to detect an increase in total plasma fatty acids from 8.5 to 10.5 mmol/L with a standard deviation of 2.8%, will provide 88% power to detect an increase in fecal elastase of 120 ug/g stool with a standard deviation of 150 ug/g stool, and will provide 85% power to detect a decrease in fecal calprotectin of 30 ug/g stool with a standard deviation of the change of 40 ug/g stool. We previously demonstrated a 3-month increase in plasma total fatty acids of this magnitude in subjects with CF receiving a fat-based nutritional supplement¹⁹. Davies et al⁶ demonstrated a change of 100 ug/g stool in fecal elastase with 24-week ivacaftor treatment in for 2 to 5 year old children with CFTR gating mutations in the KIWI study, and an even greater increase of 164 ug/g stool fecal elastase was shown in 1 to 2 year old children participating in the ARRIVAL study¹⁶. We have previously demonstrated a 3-month decrease of 30 ug/g stool in fecal calprotectin with ivacaftor treatment in 5 to 61 year old people with CFTR gating mutations⁷. The standard deviations of 9% for SEE, 40 ug/g stool for fecal calprotectin, 150 ug/g stool for fecal elastase and 0.4 for BMI Z score are reasonable estimates of the variability expected in changes for these variables from our experience with 3-12 month changes in these measures in previous longitudinal clinical trials we have conducted for changes in children and adults with CF^{7,18,19,37,38}. In addition, our recent experience with SEE measures in 1 year old healthy children showed a standard deviation of 8% in SEE percent predicted values³⁹ (personal communication).

We plan for up to 12% attrition over the 12 weeks. By enrolling 18 subjects we can account for attrition and also allow for the possibility of greater variability in the SEE, BMI Z scores and gut health and function measures.

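### Does the lack of a make-up day for the 6-week sleeping energy expenditure test leave the analysis plan exposed?

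*Combined protocol and SAP*

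**What the plan says.** All references are to the combined protocol and SAP.

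- **Measurement.** Section 5.1.3 requires SEE at every protocol visit, with the child asleep. Section 4.2.2 places the 6-week test on Day 2, during a morning nap or, failing that, an afternoon nap.
- **Reserve day at Visits 1 and 3.** Section 4.2.1 lists "Day 3 (if needed and expected for half of subjects"), to be used for SEE "if it was not performed on Day 2". Section 4.2.3 repeats this for the 12-week visit.
- **No reserve day at Visit 2.** Section 9.6 sets one payment for the 6-week visit "as an additional day will not be an option", and its table footnote repeats the point: "as there is no additional day option". Section 4.3 permits no unscheduled visits.
- **Local families.** Section 4.2 says that "for Visits 2 and 3, Days 1 and 2 can be combined to complete study protocol procedures". Section 3.3.1 has families commit to as many as two days for Visit 2.
- **Analysis.** The synopsis compares baseline with 12 weeks by a paired t-test or the signed-rank test. Section 6.1.1 adds that "mixed effects longitudinal models will be performed to assess change over all three time points (baseline, 6 and 12 weeks"), with age, sex and adherence as possible covariates. Section 1.1 gives the 6-week visit the purpose of exploring how fast the outcomes change.
- **Planned loss.** Section 6.2: "We plan for up to 12% attrition over the 12 weeks". This covers children who leave the study, not single tests that fail.

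**The concern.** The sponsor expects half of the children to need a further day for SEE at Visits 1 and 3. The wording about an afternoon nap is the same at Visits 2 and 3, so that fallback does not remove the expectation. If the same share applied at Visit 2, about 8 of 16 completers would have no 6-week SEE.

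The plan has no rule for them. An analyst who kept only children with all three values would shrink the model's sample and weaken its 12-week estimate as well. The choice could also be made after the data were seen. In addition, local families who combine Days 1 and 2 appear to leave unused a day they had already agreed to.

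**Working it through.** **Inputs.** From section 6.2: 16 evaluable children, SD of change 9 points, target fall 7 points, two-sided alpha 0.05, stated power 86%. Assumed: the same SD of change at 6 weeks, equal correlation rho between any two visits (0.3 to 0.9), values missing at random, and 25% or 50% of 6-week values missing (m = 4 or 8).

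**Step 1: the plan's own figure.** By the normal approximation, 7 × √16 / 9 = 3.111, and Φ(3.111 − 1.960) = 87.5%, within two points of the stated 86%. The exact paired t-test gives 82.8%. Both use only the baseline and 12-week values, so neither depends on Visit 2.

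**Step 2: 12-week change in a mixed model using all available values.** Every completer has both values, so the variance is 81/16 = 5.0625 and the SE is 2.25 for any m. The half-width is t(0.975, 15) × 2.25 = 2.131 × 2.25 = 4.8.

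**Step 3: 6-week change in the same model.** With residual variance 81/2 = 40.5, generalised least squares gives

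Var = [40.5/(1 + rho)] × [(1 + 2·rho)/(16 − m) + 1/16].

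At m = 0 this reduces to 81/16 for any rho, as it should.

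| m | Variance, rho = 0.3 | Variance, rho = 0.9 | SE | 95% half-width |
|---|---|---|---|---|
| 0 | 5.06 | 5.06 | 2.25 | 4.80 |
| 4 | 31.15 × (0.1333 + 0.0625) = 6.10 | 21.32 × (0.2333 + 0.0625) = 6.31 | 2.470 to 2.511 | 5.26 to 5.35 |
| 8 | 31.15 × (0.2000 + 0.0625) = 8.18 | 21.32 × (0.3500 + 0.0625) = 8.79 | 2.860 to 2.965 | 6.10 to 6.32 |

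A simulation of a random-intercept model (300 runs per case, between-child SD assumed to be 8) agrees. The median 6-week SE was 2.26, 2.49 and 2.95 at 0%, 25% and 50% missing. The 12-week SE stayed between 2.24 and 2.26. Using 15 degrees of freedom is slightly cautious: the model's own 2 × 15 = 30 give 4.6 rather than 4.8 with nothing missing.

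**Step 4: the complete-case alternative.** If children without a 6-week value were dropped, the SE of the 12-week change would be 9/√12 = 2.598 or 9/√8 = 3.182. With the model's 2(n − 1) degrees of freedom, the half-widths are about 5.4 and 6.8, against 4.6 with all 16. The plan does not propose this fit.

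**Step 5: a next-day return for local families.** Section 1.1 assumes one third of children are local. If every local return succeeded, m would fall from 4 to 2.67 or from 8 to 5.33. The half-width would become 5.08 to 5.14 or 5.48 to 5.61. The gain is about 0.2 points in the first case and at most 0.7 in the second. If only half of the returns succeeded, the half-widths would be 5.17 to 5.24 or 5.75 to 5.92.

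**The case for a change.** The best argument for a change is that it costs almost nothing. One sentence in section 6.1.1 would fix the handling in advance, and a count of tests attempted and obtained would show readers how many values support the 6-week estimate. Nap failure may also depend on the child's age or state, so missing at random is not certain.

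Part of this stands: the rule is unstated, and reporting completeness is good practice. But an analyst fitting the named model by likelihood keeps these children without being told, and nothing in the plan points to a complete-case fit. Age is already among the possible covariates.

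The 50% figure is also not a nap failure rate. It is the share expected to need Day 3 because SEE was not done on Day 2, for whatever reason, and it is stated for the two longer visits only.

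The point about local families rests on an uncertain reading. At Visits 1 and 3 the additional day in section 9.6 is Day 3. Read the same way, its absence at Visit 2 need not bar the second day allowed by section 3.3.1. Section 9.6 also says that Visit 2 needs one day of procedures, so the text can be read either way. On either reading, a return would take extra staff and metabolic-cart time, and a second trip for families living up to 150 miles away.

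**Conclusion.** The facts are as described: Visit 2 has no further day for SEE, and section 6 has no explicit rule for a missing 6-week value. Neither calls for a change. The missing rule is a detail that the named model fills sensibly. The shorter visit is a deliberate trade-off that spares families a day for an exploratory time point.

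The paired baseline-to-12-week SEE test, its power and the BMI Z score analysis are untouched. The loss is confined to the 6-week SEE estimate, whose half-width rises by about 0.5 points at 25% missing and 1.3 to 1.5 points at 50%. A local return day would recover 0.2 to 0.7 points at best.

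These sizes rest on 16 completers, an SD of change of 9 at both visits, equal correlations, values missing at random, and failure rates that the documents do not supply.
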